9.3.3. Multiple Comparisons and Multiplicity

As this is an early-phase exploratory study, no adjustment for multiple comparisons will be made. Treatment comparisons will be presented as effect sizes with 95% confidence intervals.

9.4. Key Elements of Analysis Plan

Each subject will undergo two treatment periods in this crossover study, each one of which being subdivided into five key sub-epochs (labelled T0-T4) as follows:

- T0: Pre-dose (period baseline)
- T1: Post-dose, normoxic, at rest, pre-challenge
- T2: Hypoxic, at rest
- T3: Hypoxic, immediately after exercise (for Part 2, echo data will be measured during exercise)
- T4: Post-challenge, normoxic, at rest

This follows the principle illustrated in the diagram of echocardiograph measurements ([Figure 2](#)).

PASP and Oxygen Saturation will be assigned to T0 thru T4 timepoints based on when they happened relative to the sequence of events that the subject undertakes during the course of the study day. Biomarkers will be collected at times T0 thru T4, plus additional timepoints.

Pharmacokinetic endpoints will be timed based on elapsed time since dose administration.

In addition to T0 being defined as the period baseline, an overall subject baseline will be defined as the mean of the two T0 measurements (one from each period).

Change from baseline at time points T1 - T4 will be calculated as the difference between the measurement at the time point in question and the period baseline. Separate statistical analyses will be conducted for subjects in Part 1 and Part 2 of the study. In general, statistical modelling of changes from baseline will be done using a Bayesian mixed effects regression model, including covariates for period, treatment, period baseline and subject baseline (the mean of the two period baselines). Subject will be fitted as a random effect and non-informative priors will be used for model parameters. An unstructured covariance structure within each subject-period-treatment cell will be assumed to account for repeated measurements.

Bayesian mixed effects regression models (as described above) will be fitted (using non-informative priors for the model parameters), and an estimate of the mean change from baseline in PASP for each treatment group and post-baseline timepoint, together with its 95% credible interval, will be obtained. Estimates for treatment differences will also be presented. Data may be log-transformed if necessary.

PASP data will be summarized separately by Part 1 and Part 2 by treatment and time-point in tabular and graphical format.

Details of the analysis of other endpoints will be described in the RAP.

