2. INTRODUCTION

GSK2586881 is a purified intravenous formulation of soluble recombinant human angiotensin converting enzyme type 2 (rhACE2), which is expressed in Chinese Hamster Ovary cells. Angiotensin converting enzyme type 2 (ACE2) is a zinc carboxypeptidase involved in the Renin-Angiotensin System (RAS) that controls blood pressure, electrolytes, and intravascular fluid volume. A key function of ACE2 is believed to be the cleavage of Angiotensin II (Ang II) to Ang (1-7), which have opposing physiological roles. Elevated levels of Ang II are associated with vasoconstriction, inflammation, fibrosis, vascular leak, and sodium absorption. Ang (1-7) appears to be a counter-regulatory protein in the RAS; associated with vasodilation, anti-proliferation, anti-inflammation, and reduced vascular leak, as noted in [Figure 1](#) below [Paul, 1992; Santos, 2005; Suzuki, 2003].

Figure 1 Renin Angiotensin System

Ang II binds to two distinct receptors called AT-1 and AT-2, with the AT-1 receptor mediating the vasoconstrictive, proliferative and pro-inflammatory actions of Ang II. The function of the AT-2 receptor has not been fully elucidated. Ang (1-7) initiates its effects by binding to the Mas-receptor, and also acts by inhibiting the activity of the carboxyterminal domain of angiotensin converting enzyme (ACE), which prevents ACE from fully acting on its substrates Angiotensin I and bradykinin.

ACE and Angiotensin II has been implicated in the pathogenesis of acute respiratory distress syndrome (ARDS), and pulmonary hypertension. It has been observed that circulating Ang II levels and lung ACE levels are increased in humans with ARDS and pulmonary hypertension. It has also been shown that the DD ACE polymorphism, which is associated with higher ACE activity, is associated with susceptibility to development of lung injury and worsened outcome (mortality) in patients with ARDS [[Marshall, 2002](#)] and to the development of pulmonary hypertension [[Abraham, 2003](#)].

It is expected that the reduction of Ang II and simultaneous formation of Ang (1-7) should have positive impacts in ARDS and on pulmonary haemodynamics in patients with pulmonary hypertension. This dual action can be achieved by ACE2, and thus, an

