3. OBJECTIVE(S) AND ENDPOINT(S)

Objectives	Endpoints
Primary	

 To evaluate the effect of a single IV dose of GSK2586881 on the HPV response in healthy volunteers during exercise under hypoxic conditions. 	
 Change from baseline of Pulmonary Artery Systolic Pressure (PASP) measured via Echocardiography.
Secondary	

 To evaluate the effect of a single IV dose GSK2586881 on RAS peptide responses. To evaluate the safety of a single IV dose of GSK2586881 in healthy volunteers. To evaluate the pharmacokinetics of a single IV dose of GSK2586881. 	
 Effect of GSK2586881 on baseline levels and changes in response to hypoxia and exercise of RAS peptides (e.g. Ang II, Ang(1-7), Ang(1-5)). Vital signs (heart rate, systolic and diastolic blood pressure), oxygen saturation, 12-lead ECGs, AEs, immunogenicity and clinical laboratory assessments and continuous pulse oximetry. Plasma concentrations of GSK2586881 and derived pharmacokinetic parameters.
Exploratory	

 To evaluate the effect of a single IV dose of GSK2586881 on ventilatory parameters in healthy volunteers during exercise in hypoxic conditions. To evaluate the pharmacodynamic activity of a single IV dose of GSK2586881 in healthy volunteers during exercise in hypoxic conditions. To evaluate Pharmacogenetics. To evaluate the effect of a single IV dose of GSK2586881 on the HPV response in healthy volunteers under hypoxic conditions (and during exercise under hypoxic conditions). 	
 Change from baseline of oxygen consumption (VO₂), carbon dioxide production (CO₂) and other parameters as data permit. Change from baseline in Surfactant Protein (SP-D) and/or additional analytes to be determined. Evaluate I/D polymorphisms in the Angiotensin Converting Enzyme (ACE) gene and analyse the impact on Ang II (and possibly other RAS peptides), hypoxic pulmonary vasoconstriction and responses to GSK2586881 administration. Estimation of pulmonary vascular resistance (PVR) measured via echocardiography.

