9. STATISTICAL CONSIDERATIONS AND DATA ANALYSES

9.1. Hypotheses

The focus of this study is on the exploration of the effect of GSK2586881 on a range of echocardiography, pulse oximetry, biomarker, safety and PK endpoints, when subjecting healthy volunteers to an exercise challenge under hypoxic conditions. No formal statistical hypotheses are being tested. A Bayesian statistical analysis framework with non-informative priors for model parameters (unless otherwise specified) will be used to obtain posterior distributions for effects of interest for Part 1 and Part 2 of the study. These posterior distributions will be used to obtain a number of probability statements about the magnitude of treatment effects (e.g. Probability of **any** treatment related reduction in PASP, or Probability that the treatment related reduction in PASP ≥ 5 mmHg).

A rule of thumb for end of “study success” is if the probability of any treatment related reduction in PASP (T3-T0) exceeds 0.95 (success is also conditional on the probability of (absolute) treatment related reductions in oxygen saturation exceeding 5%, being small).

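### T3 minus pre-dose T0 mixes a resting drug effect on PASP with a change in the hypoxic response; add T2-T1 and T3-T1 and read the HPV conclusion beside them

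*Protocol*

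**What the plan says.** Section 3 of the protocol sets the primary objective as the effect of a single dose "on the HPV response in healthy volunteers during exercise under hypoxic conditions". The matching endpoint is "Change from baseline of Pulmonary Artery Systolic Pressure (PASP) measured via Echocardiography".

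Section 9.4 labels five echo time points. T0 is taken before dosing and is the period baseline. The next is "T1: Post-dose, normoxic, at rest, pre-challenge". T2 is hypoxia at rest, T3 is hypoxia with exercise, and T4 is back at rest in normoxia. Change at T1 to T4 "will be calculated as the difference between the measurement at the time point in question and the period baseline". The model covariates are period, treatment, period baseline and subject baseline, the last two built from T0 only.

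Section 9.1 gives a rule of thumb for success: the "probability of any treatment related reduction in PASP (T3-T0) exceeds 0.95". It carries a second condition, that the probability of an absolute saturation reduction of more than 5% is small. The Analysis part of the synopsis names the T3 comparison as the most important posterior statement. It also plans drug versus placebo posteriors at each of T1 to T4. Parts 1 and 2 are analysed separately.

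**The concern.** A response to hypoxia is a rise from the state just before the challenge. On active drug that state is T1, after dosing, and not T0. If the drug lowers PASP at rest in normoxia and leaves the rise alone, T3-T0 is smaller on drug than on placebo, and the contrast reads as a blunted HPV response.

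A resting effect is conceivable from the protocol's own background: Section 2 describes Ang(1-7), the product of the enzyme, as "associated with vasodilation, anti-proliferation, anti-inflammation, and reduced vascular leak".

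The distinction bears on the reason for the trial. Section 2.1 treats blunted HPV as a possible threat to oxygenation in ARDS, and reads reduced HPV without extra hypoxaemia as support for use in pulmonary hypertension. A general lowering of PASP with HPV intact would give that same pattern: lower T3-T0 and no loss of saturation. The saturation condition therefore cannot tell the two apart.

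**Working it through.** **1. Reproduce the plan's precision.** Inputs from Section 9.2.1: SD 2.81 mmHg at rest and 4.30 mmHg under hypoxia and exercise; within-subject correlation ρ of 0, 0.3, 0.6 or 0.9. The equal correlation for all pairs of measurements is stated in Section 9.3.2.1. Simulating the described model (3000 runs per cell, N-3 degrees of freedom) gives 95% half-widths at N=20 of 2.78 / 2.40 / 1.82 / 0.91. Table 3 has 2.76 / 2.40 / 1.83 / 0.91. All 16 cells agree within about 1.5%, so Table 3 is right for the contrast it describes.

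**2. Split the contrast.** Let *a* be the drug effect on resting PASP, and *b* its effect on the hypoxic and exercise rise.

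- Effect on T3-T0 = *a* + *b*.
- Effect on T1-T0 = *a*.
- Effect on T3-T1 = *b*, if *a* is the same at T1 and T3.

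Example with the protocol's means of 30 and 45 mmHg, *a* = -5 and *b* = 0:

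| | T0 | T1 | T3 | T3-T0 | T3-T1 |
|---|---|---|---|---|---|
| Placebo | 30 | 30 | 45 | +15 | +15 |
| Drug | 30 | 25 | 40 | +10 | +15 |
| Difference | | | | -5 | 0 |

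T3-T0 shows 5 mmHg, the protocol's rough guide to a clinically meaningful difference, with no effect on the response.

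**3. How often the PASP part of the rule would be met with *b* = 0.** Assumptions not in the documents: the size of *a*; a parallel shift at T1 and T3; T1 with SD 2.81 and the same ρ. The flat-prior posterior probability is taken as a one-sided t probability.

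With both T0 values as covariates:

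- SE(T3-T0) = 4.30 × √(2(1-ρ)/N). At N=10, ρ=0.6: 4.30 × √0.08 = 1.22. Times t = 2.365 on 7 df, the half-width is 2.88; Table 3 has 2.92.
- SE(T3-T1) = √(4.30² + 2.81²) × √(2(1-ρ)/N). At N=10, ρ=0.6: 5.14 × √0.08 = 1.45.
- Ratio: √(4.30² + 2.81²) / 4.30 = 1.195.

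Probability of meeting the 0.95 threshold, from the non-central t with N-3 df and non-centrality *a*/SE in absolute value:

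| N | ρ | SE(T3-T0) | shift 2 mmHg | shift 5 mmHg | no shift |
|---|---|---|---|---|---|
| 10 | 0.3 | 1.61 | 0.30 | 0.87 | 0.05 |
| 10 | 0.6 | 1.22 | 0.44 | 0.98 | 0.05 |
| 14 | 0.3 | 1.36 | 0.40 | 0.96 | 0.05 |
| 14 | 0.6 | 1.03 | 0.57 | 0.998 | 0.05 |

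Ten is the number of Part 1 completers at the interim analysis; 14 is the Part 2 enrolment limit.

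**4. Check by simulation.** At N=14 a shift of 2.5 mmHg met the rule in 0.51 (ρ=0.3) and 0.71 (ρ=0.6) of runs; the formula gives 0.53 and 0.74. Using T3-T1, shifts of 2.5 or 5 mmHg met it in 0.04 to 0.06.

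**5. Price in precision.** At N=20 the half-width rises from 2.44 to 2.91 (ρ=0.3) and from 1.85 to 2.21 (ρ=0.6). With a true 5 mmHg HPV effect at N=14, the chance of meeting the threshold is 0.95 on T3-T0 and 0.87 on T3-T1 (ρ=0.3), or 0.995 and 0.98 (ρ=0.6).

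**The case against.** The case on the other side is substantial, and most of it stands.

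- **T1 is analysed.** A reader might infer that the T1 echo goes unused and that a resting effect would pass unnoticed. The documents do not support that. Posteriors and treatment differences are planned at every post-dose time point, so T1-T0 estimates the resting effect directly and T2-T0 stands beside it. What is missing is a link from these to the HPV conclusion; two separate posteriors also do not give the posterior of their difference.
- **The success criterion is soft.** Section 9.1 calls it a rule of thumb, tests no formal hypothesis and adds the saturation condition. A reader might take any PASP reduction alone as success, which misstates it. The saturation analysis does address oxygenation, but it does not separate *a* from *b*.
- **No resting effect is documented.** Section 2 speaks of an association with vasodilation, and Section 4.5 predicts a lowering of raised, ARDS-level Ang II. Neither predicts lower resting PASP in healthy volunteers with normal screening PASP. To say that the protocol expects one overreads it.
- **T3-T1 is not a pure measure of HPV.** T1 is about 15 minutes after dosing and T3 about 90 (chamber entry near 30 minutes, exercise from 60 minutes after entry). T3 adds exercise and, in Part 2, a semi-recumbent tilted posture. The contrast removes the resting effect only if that effect is additive and constant over this span.
- **Extra contrasts are often left to the analysis plan.** That is so, but the change definition, the rule of thumb and the leading posterior are fixed in the protocol, and the point concerns what they estimate.

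Part 2 also adds an exploratory echo estimate of pulmonary vascular resistance. It may help interpretation, but it too is not tied to the conclusion.

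**Conclusion.** The point holds as a cheap improvement. T3-T0 estimates the resting effect plus the change in the hypoxic and exercise rise, while the objective names only the response. That follows from the definitions and needs no assumption about size.

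The size does rest on assumptions: a parallel shift of 2 to 5 mmHg, the protocol SDs, equal correlation of 0.3 to 0.6, and T1 as variable as T0. On these, the PASP part of the rule would be met with probability about 0.30 to 0.98 at N=10 and 0.40 to 0.998 at N=14 with HPV unchanged, against 0.05 with no shift. The figures show what could happen; they do not show that the drug lowers resting PASP.

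A reader might go on to infer that T3-T0 is invalid as the primary comparison, or that T3-T1 should replace it. Neither follows, because T3-T1 has its own untested assumption and wider intervals.

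**What to change.** Keep T3-T0 as the primary comparison. In Section 9.4, add two between-treatment contrasts from the same repeated-measures model, each with its posterior probabilities:

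- T2-T1, the cleaner one, since it compares hypoxia with normoxia at rest;
- T3-T1.

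State that any wording about modulation of HPV is to be read with these contrasts and with the T1-T0 comparison. Note beside T3-T1 that it assumes a resting effect that is additive and constant from T1 to T3, and that T3 also includes exercise and, in Part 2, a different posture.

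The cost is two lines of output from echoes already taken, with no new procedure or subject. The interval for T3-T1 is about 19-20% wider than for T3-T0 under the assumed T1 SD and correlation. The primary comparison loses nothing.

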9.4.1. Pharmacokinetic Analyses

Pharmacokinetic analysis will be performed by, or under the auspices, of Clinical Pharmacology Modelling and Simulation Department within GlaxoSmithKline. Plasma GSK2586881 concentration-time data will be analysed by non-compartmental methods with WinNonLin V6.3 or greater. Calculations will be based on the actual sampling times recorded during the study.

From the plasma concentration-time data, the following pharmacokinetic parameters will be determined, as data permit: maximum observed plasma concentration (Cmax), time to Cmax (tmax), area under the plasma concentration-time curve over the study period [nominally AUC(0-2.5h) post-dose], AUC over the hypoxia challenge (nominally AUC(0.5-2.0h post-dose), plasma clearance (CL), volume of distribution (V) and apparent terminal phase half-life (t1/2), if data permit. Other PK parameters may also be determined.

Pharmacokinetic data will be presented in graphical and/or tabular form and will be summarized descriptively by Part 1 and Part 2. All pharmacokinetic data will be stored in the Archives, GlaxoSmithKline Pharmaceuticals, R&D.

The relationship between the RAS biomarkers and other pharmacodynamic endpoints (echocardiography and pulse oximetry) and GSK2586881 concentrations and/or PK parameters may also be explored for Part 2, if appropriate.

If appropriate, a population PK analysis may also be conducted, in addition the plasma concentration-time data may be merged with historical data and analysed as part of a population PK meta-analysis.

10. STUDY GOVERNANCE CONSIDERATIONS

10.1. Posting of Information on Publicly Available Clinical Trial Registers

Study information from this protocol will be posted on publicly available clinical trial registers before enrollment of subjects begins.

10.2. Regulatory and Ethical Considerations, Including the Informed Consent Process

Prior to initiation of a site, GSK will obtain favourable opinion/approval from the appropriate regulatory agency to conduct the study in accordance with ICH Good Clinical Practice (GCP) and applicable country-specific regulatory requirements.

The study will be conducted in accordance with all applicable regulatory requirements, and with GSK policy.

The study will also be conducted in accordance with ICH Good Clinical Practice (GCP), all applicable subject privacy requirements, and the guiding principles of the current version of the Declaration of Helsinki. This includes, but is not limited to, the following:

- IRB/IEC review and favorable opinion/approval of the study protocol and amendments as applicable
- Obtaining signed informed consent
- Investigator reporting requirements (e.g. reporting of AEs/SAEs/protocol deviations to IRB/IEC)
- GSK will provide full details of the above procedures, either verbally, in writing, or both.
- Signed informed consent must be obtained for each subject prior to participation in the study
- The IEC/IRB, and where applicable the regulatory authority, approve the clinical protocol and all optional assessments, including genetic research.
- Optional assessments (including those in a separate protocol and/or under separate informed consent) and the clinical protocol should be concurrently submitted for approval unless regulation requires separate submission.
- Approval of the optional assessments may occur after approval is granted for the clinical protocol where required by regulatory authorities. In this situation, written approval of the clinical protocol should state that approval of optional assessments is being deferred and the study, with the exception of the optional assessments, can be initiated.

10.3. Quality Control (Study Monitoring)

- In accordance with applicable regulations including GCP, and GSK procedures, GSK monitors will contact the site prior to the start of the study to review with the site staff the protocol, study requirements, and their responsibilities to satisfy regulatory, ethical, and GSK requirements.
- When reviewing data collection procedures, the discussion will also include identification, agreement and documentation of data items for which the CRF will serve as the source document.
- Source documents provide evidence for the existence of the participant and substantiate the integrity of the data collected. Source documents are filed at the investigator's site.
- Data entered in the eCRFs that are transcribed from source documents must be consistent with the source documents or the discrepancies must be explained. The investigator may need to request previous medical records or transfer records, depending on the study; also current medical records must be available.

GSK will monitor the study and site activity to verify that the:

- Data are authentic, accurate, and complete.
- Safety and rights of subjects are being protected.
- Study is conducted in accordance with the currently approved protocol and any other study agreements, GCP, and all applicable regulatory requirements.

The investigator and the head of the medical institution (where applicable) agrees to allow the monitor direct access to all relevant documents

10.4. Quality Assurance

- To ensure compliance with GCP and all applicable regulatory requirements, GSK may conduct a quality assurance assessment and/or audit of the site records, and the regulatory agencies may conduct a regulatory inspection at any time during or after completion of the study.
- In the event of an assessment, audit or inspection, the investigator (and institution) must agree to grant the advisor(s), auditor(s) and inspector(s) direct access to all relevant documents and to allocate their time and the time of their staff to discuss the conduct of the study, any findings/relevant issues and to implement any corrective and/or preventative actions to address any findings/issues identified.

10.5. Study and Site Closure

- Upon completion or premature discontinuation of the study, the GSK monitor will conduct site closure activities with the investigator or site staff, as appropriate, in accordance with applicable regulations including GCP, and GSK Standard Operating Procedures.
- GSK reserves the right to temporarily suspend or prematurely discontinue this study at any time for reasons including, but not limited to, safety or ethical issues or severe non-compliance. For multicenter studies, this can occur at one or more or at all sites.
- If GSK determines such action is needed, GSK will discuss the reasons for taking such action with the investigator or the head of the medical institution (where applicable). When feasible, GSK will provide advance notification to the investigator or the head of the medical institution, where applicable, of the impending action.
- If the study is suspended or prematurely discontinued for safety reasons, GSK will promptly inform all investigators, heads of the medical institutions (where applicable) and/or institution(s) conducting the study. GSK will also promptly inform the relevant regulatory authorities of the suspension or premature discontinuation of the study and the reason(s) for the action.
- If required by applicable regulations, the investigator or the head of the medical institution (where applicable) must inform the IRB/IEC promptly and provide the reason for the suspension or premature discontinuation.

